6.2 PREPARATION/HANDLING/STORAGE/ACCOUNTABILITY

6.2.1 ACQUISITION AND ACCOUNTABILITY

NR and matching placebo will be obtained from ChromaDex, Irvine, CA. NR is manufactured in a Good Manufacturing Practice (GMP)-compliant facility according to ISO/IEC 18025:2005 standards.

For all study drugs (NR and placebo), a system of numbering in accordance with all requirements of Good Clinical Practice (GCP) will be used, ensuring that each dose of study drug can be traced back to the respective batch of the ingredients. Lists linking all numbering levels will be maintained by the PI. A complete record of batch numbers and expiry dates of all study treatment as well as the labels will be maintained in the study file.

Following randomization of a participant, a computer-generated system will generate randomization number, medication numbers, and treatment code. During the hospital stay the hospital nursing staff will administer drug to a participant as prescribed: 2 capsules of each 250 mg orally every 12 hours and document the administration in compliance log. The local hospital research pharmacist will prepare study drug for nasogastric tube administration as per guidelines from ChromaDex.

Participants with hospital stay of <10 days will be provided with study drug in a pill box at the time of discharge to maximize compliance for the remaining days. These participants will receive clear verbal and written instructions on administering of and compliance with study drug.

All expired and unused products will be returned to supplier ChromaDex for destruction. 6.2.2 FORMULATION, APPEARANCE, PACKAGING, AND LABELING

NR is supplied as capsule white in color and each capsule contains active ingredient nicotinamide riboside chloride 250 mg. Placebo capsules will be identical in appearance (size, shape, color). The study drug will be labeled as required by law: Caution: New Drug. Limited by Federal Law to Investigational Use.

Preparation of NR or matching placebo for administration via nasogastric tubing will be prepared daily, as needed, in an aqueous suspension in 100 ml of water and will be made by each local hospital research pharmacist.

6.2.3 PRODUCT STORAGE AND STABILITY

All study drugs will be stored at the respective site hospital Research Pharmacy and will follow GCP and GMP requirements. Study drugs will be inaccessible to unauthorized personnel. Both NR and placebo are stable at room temperature. Storage conditions (minimum and maximum temperatures) and a complete record of batch numbers and expiry dates will be maintained in the study file.

Participants discharged before completing 10-day in-hospital intervention will store study drug at home in a cool dark place at temperature below 25°C preferably in a refrigerator.

6.2.4 PREPARATION

If participants require nasogastric tube administration, NR will be available in a powder form and the NR and placebo will be prepared by pharmacist so that both solutions are not visually distinguishable.

Both NR and placebo will be available in capsule form for oral administration. NR or matching placebo will be administered via nasogastric tube to those participants who are intubated or felt to be at aspiration risk. Hospital research pharmacist will prepare the nasogastric preparation for both NR and matching placebo. The pharmacist will weigh out and prepare the bulk NR or matching placebo powder in purified water immediately before administration. Powder NR yields slight yellowish-brown color when dissolved in water. To mask this, pharmacist will dissolve brown sugar in water. For example, to match 1 gram of Niagen in 50 mLs of purified water, placebo will be prepared by dissolving ~75 mgs of brown sugar in 50 mLs of purified water for administration via NG tube.

6.3 MEASURES TO MINIMIZE BIAS: RANDOMIZATION AND BLINDING

Eligible participants who provide voluntary consent will advance to randomization. In order to minimize bias, the set inclusion and exclusion criteria offer broader participation from a wider range of participants who may be eligible in three geographically diverse study centers. The set of inclusion and exclusion criteria do not compromise the scientific integrity.

The study drug (NR or placebo) packaging and labeling will be designed to maintain the blinding of the investigator's team and the participants. The study drug allocation will remain blinded to the study participants and study investigators according to standard operating procedures. The randomization and blinding procedures will be described in a corresponding manual of operation (MOP).

If participants require nasogastric tube administration, NR will be available in a powder form and the NR and placebo will be prepared by pharmacist so that both solutions are not visually distinguishable. Using a dark opaque sterile draping the participant will not visually perceive the NG administration of study drug. The hospital nurse will administer the nasogastric feeding and use an opaque sterile draping so participant and study personnel will not visually perceive the drug administration of study drug.

Under normal circumstances, the blind should not be broken until all participants have completed the study and the database is finalized. However, the treatment blind may be broken to provide unblinded information to the study site only if specific emergency treatment/course of action would be dictated by knowing the treatment status of the participant. In the event of an emergency or any finding that requires unblinding, the investigator may break the blind for an

individual participant. This will allow the investigator, or other responsible person, to identify the study drug if there is an emergency, without jeopardizing the double-blind integrity of the remainder of the study. The code can be broken by the investigator, or other responsible person, when knowledge of the participant's treatment is required for the clinical management of the participant. If it becomes necessary to know the individual treatment during the study and thus to break the code for that participant, the date and reason for unblinding are to be recorded on the relevant source document and in the REDCap eCRF.

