5.5 STRATEGIES FOR RECRUITMENT AND RETENTION

Participants will be recruited from three participating sites: the University of Texas Health San Antonio (UTHSA), Icahn School of Medicine at Mount Sinai, New York, NY, and University of Washington (UW), Seattle, WA. The single IRB (sIRB) at the Washington University in St. Louis (FWA00002284) will serve as the Central IRB for all three participating sites. We will recruit and consent eligible participants and will advance them into the Treatment Period. A total of 100 participants will be randomized.

Each participating site and the coordinating site (UTHSA) will contribute to recruitment of study participants. Recruitment methods will focus primarily on the selection of eligible participants via identifying patients admitted to the respective hospitals with a diagnosis of COVID-19. Lead investigators at each site are physician scientists who will have direct access to eligible participants. For efficient recruitment, each site will employ the following approaches. After a COVID-19 patient is admitted to the hospital with a new positive laboratory diagnosis of COVID-19, the study team members will be notified by the COVID-19 Admitting Team. All

three participating sites also maintain a COVID-19 database which is updated every 6-8 hours and a designated study member will review the COVID-19 database twice a day. Each study team will have access to the respective hospital COVID-19 admission logs and EHR enabling them to review several eligibility criteria. The study investigators or clinical coordinators will approach the potentially eligible participants or LAR (when appropriate) and inform them of the study protocol. All participants will provide written consent for participation in the study. Sites have the ability to use one of the FDA approved options for obtaining written signature during a pandemic, based on their institutional requirements.

During consenting process, each participant will receive clear and detailed information about the NIRVANA study with an emphasis on risks, benefits, and alternative to enrollment. Participants will be given opportunities and time to learn about ongoing clinical trials for COVID-19 and their eligibility to enroll in another competing study. Voluntary participation will be discussed and participants will be allowed to withdraw from the current study at any time point after providing consent.

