6 STUDY INTERVENTION

6.1 STUDY INTERVENTION(S) ADMINISTRATION

6.1.1 STUDY INTERVENTION DESCRIPTION

Baseline Visit (Day 1)

After obtaining consent, baseline visit procedures will be performed as listed in Table 1 (Schedules of Activities in Section 1.3). Participants will be randomized after abstracting the following data from the EHR: sociodemographic, contact information, medical/surgical history,

comorbidities, and routine medications on admission, standard of care at hospital, home medications, all concomitant medicines including dietary or nutritional supplements and over-the-counter medications, vitals and physical examinations, routine laboratory test results.

Randomization will be accomplished through the use of an online randomization service. Participants will be randomly allocated to 1:1 ratio to receive either nicotinamide riboside (NR) or placebo. Only the study statisticians (Drs [name] and [name]) and the local hospital Research Pharmacists will have access to the randomized assignment for the purpose of tracking randomization and study drug dispensing, respectively. Study investigators and study participants will be blinded to the intervention assignments. Neither the statisticians nor the pharmacist will have direct contact with the study participants.

Eligible study participants enter intervention phase after consenting to the study protocol:

- Nicotinamide riboside (NR, Niagen[®]) or placebo will be administered orally (or via nasogastric tube) 500 mg twice a day for 10 days during hospitalization or prescribed for at home administration if discharged before 10 days from the hospital.
- Placebo capsule manufactured by ChromaDex to match NR or Niagen®

TREATMENT PERIOD

All measures related to study treatment visits are harmonized to standard of care to minimize care interruption and disruption to hospital staff workflow. Most of the treatment procedures are standard of care or routine procedures for COVID-19 participants in an acute care setting. These data will be obtained from the EHR. If any treatment procedure is not available through the EHR, the study team will obtain these data from the primary care team or directly from the participant. Where multiple results are present in the EHR, they will all be recorded in the study database so that all relevant values are captured. A summary of the trial's schedule of event is included in Table 1 (Section 1.3).

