7.2 PARTICIPANT DISCONTINUATION/WITHDRAWAL FROM THE STUDY

Participants are free to withdraw from participation in the study at any time upon request, for any reason, and without any consequence. Participants should be listed as having withdrawn consent only when they no longer wish to participate in the study and no longer authorize the investigators to make efforts to continue to obtain data. A participant has a right to withdraw from the current study and enroll in a different research study at any time point. However, participants will remain in the current study and all data will be collected as per the Schedule of Activities (section 1.3), Table 1 unless participants withdraw consent.

The study investigators have the right to discontinue the study drug at any time, which may be due but not limited to the following reasons:

- For an individual participant, a suspected drug-related event of hypersensitivity Grade 2 or higher;
- The investigator believes that for safety (e.g., SAE) or tolerability reasons it is essential for the participant to stop treatment;
- The investigator formally unblinds the participant's treatment allocation for safety reasons;
- The participant requires renal replacement therapy or dialysis of any type (Note: The requirement for dialysis is the only endpoint for which treatment with double-blind study drug should be discontinued;
- The participant takes prohibited NR supplements (multivitamins are allowed);
- Newly reported results of parallel clinical studies and/or animal studies indicating toxicity, teratogenicity, carcinogenicity or reproduction toxicity of NR at similar doses administered in this study;

Participants who are permanently discontinued from receiving investigational product will be followed for protocol-specified assessments unless consent is withdrawn from further study participation, or the participant is lost to follow-up.

In the event of a study drug discontinuation due to safety and tolerability, participants will continue to receive available and/or standard management for COVID-19 and comorbidities as

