9.4 STATISTICAL ANALYSES

9.4.1 GENERAL APPROACH

In general, continuously distributed data will be summarized with the sample size, mean, standard deviation, median, minimum, and maximum. Categorical and binary data will be summarized with frequencies and percentages. Raw data storage, documentation, and security will be effectively served with the REDCap platform. Participants will be randomized to treatments in randomly permuted blocks of size 2 and 4 stratified by clinical site.

The number of participants screened, the number of screen failures by reason, and the number eligible for randomization, the number randomized, and, by treatment (Placebo, NR), the number withdrawing from the study for any reason, lost to follow-up by reason, unable to receive at least one dose and replaced, and the number completing the study per protocol will be tabulated and summarized with a CONSORT Diagram. We will also describe adherence to treatment over the course of the study, overall and by treatment arm.

Randomized controlled trials often suffer from two major complications, i.e., noncompliance and missing outcomes. One potential solution to this problem is a statistical concept called intention-to-treat (ITT) analysis, to be used in this trial. ITT analysis includes every subject who is randomized according to randomized treatment assignment. It ignores noncompliance, protocol deviations, withdrawal, and anything that happens after randomization. ITT analysis maintains prognostic balance generated from the original random treatment allocation. In ITT analysis, estimate of treatment effect is generally conservative [83].

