Adverse Events and Serious Adverse Events: Reportable AEs will be entered into the REDCap study database. Reportable AEs will be entered, classified, and graded according to the most current versions of the CTCAE by the site investigator and independent site SAC Physician. Adverse events indicated as Serious Adverse Events will result in real-time alerts through the REDCap system to support expedited reporting. Entry of reportable Adverse Events will trigger notification to the independent SAC physician to initiate the independent review and adjudication process as described in section 8.3.7. AEs will be coded at the DCC using the MedDRA controlled terminology.

Biosample Inventory and Tracking: The REDCap study database will include screens at each visit for sites to report samples obtained and shipped to the UTHSA COVID-19 Repository. Sample tracking will trigger notification to the repository. Samples received will be reconciled with REDCap biosample tracking on the day of receipt. Data status reports will flag expected and missing sample tracking data.

Data Status Reports: Enrollment data will be entered into REDCap on the day of enrollment. Enrollment entry enables tracking and management of participant data and samples and will trigger notification to the site and DCC study team. Data entry will be entered every day during the 10-day treatment period and within one week of follow-up visits. Late data will be listed on an exception report by site and by participant. Similarly, data discrepancies will be resolved within a week of firing. Late data discrepancy resolutions will be listed on an exception report by site and by patient. Data will be reviewed by the DCC within 24 hours of complete entry. The site investigator will be responsible for review of data collection tools and processes, and review of data and reports.

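### After a code break, site staff can guess the paired participant's arm with 67% to 100% probability, because Section 9.4.1 prints site blocks of 2 and 4; the assurance in Section 6.3 does not hold for that participant

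*Combined protocol and SAP*

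**What the plan says.** Section 6.3 provides for breaking the blind of an individual participant and says this allows the investigator or another responsible person "to identify the study drug if there is an emergency, without jeopardizing the double-blind integrity of the remainder of the study". It adds: "The code can be broken by the investigator, or other responsible person, when knowledge of the participant's treatment is required for the clinical management of" that participant. Section 7.2 lists, among the reasons for discontinuing study drug: "The investigator formally unblinds the participant's treatment allocation for safety reasons". Code breaks are therefore foreseen.

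Section 9.4.1 states: "Participants will be randomized to treatments in randomly permuted blocks of size 2 and 4 stratified by clinical site". Section 6.1.1 gives the ratio: "Participants will be randomly allocated to 1:1 ratio to receive either nicotinamide riboside (NR) or placebo".

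The documents do not say how often each block size is used, whether the size is drawn at random, how many code breaks are expected, or that block sizes are withheld from sites. Section 6.3 leaves further detail on randomization and blinding to a manual of operation that was not available for this review.

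**The concern.** Small even blocks within site tie each participant's allocation to that of a neighbour in the enrolment sequence. Opening one code then gives information about someone else, which is hard to square with the assurance in Section 6.3.

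Two things could be affected.

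- **Assessment.** Site investigators make the initial severity and causality assessment (Section 2.3.3), grade events (Section 8.2) and determine expectedness (Section 8.3.3.3). Under Section 8.3.5, expected events and those related to COVID-19 outcomes are not adjudicated by the Safety Adjudication Committee. Under Section 8.3.6, listed COVID-19 outcomes are exempt from reporting unless the investigator sees a definite, possible or uncertain relationship to the study drug or procedures. For such events the site's decision may get no blinded check. Graded events enter the primary safety test (Section 9.4.2), and the interim harm boundary (Section 9.4.6) also rests on them.
- **Selection.** If the code of an odd-numbered participant at a site is broken before the next enrolment, the pair-mate is the next patient, and allocation concealment for that patient is weakened. Site staff decide whom to approach (Section 5.4), and the site investigator settles uncertain eligibility (Section 5.1).

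**Working it through.** The plan gives no predictability figure, so there is none to reproduce.

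**Inputs from the documents:** 1:1 allocation (Section 6.1.1), and blocks of 2 and 4 by site (Section 9.4.1).

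**Assumptions:**
- A fraction q of the blocks has size 2. The value of q is not given.
- The person guessing knows the block sizes and has followed the site's order from its first participant. Section 10.1.8.1 makes this plausible ("Enrollment entry enables tracking and management of participant data and samples and will trigger notification to the site and DCC study team"), but it is an inference.

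**Step 1, pairs.** Both sizes are even, so participants 1 and 2, 3 and 4, 5 and 6, and so on at a site always share a block.

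**Step 2, within a block.** In a block of size b with b/2 per arm, once one member's arm is known, another member is on the opposite arm with probability (b/2)/(b − 1).
- b = 2: 1/1 = 100%
- b = 4: 2/3 = 66.7%

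With no information the figure is 50%.

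**Step 3, mixing the sizes.** The share of participants in blocks of 2 is s = 2q/[2q + 4(1 − q)] = q/(2 − q). Then P(pair-mate on the opposite arm) = s × 1 + (1 − s) × 2/3.

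| q | s | P |
|---|---|---|
| 0 (all blocks of 4) | 0 | 66.7% |
| 1/4 | 1/7 | 71.4% |
| 1/2 (equal use) | 1/3 | 7/9 = 77.8% |
| 2/3 | 1/2 | 83.3% |
| 3/4 | 3/5 | 86.7% |
| 1 (all blocks of 2) | 1 | 100% |

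A simulation of 200,000 site sequences with equal use gave 77.9%.

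**Step 4, position in the sequence.** With equal use, an exact recursion gives 83.3% for a site's first pair, 75.0% for the second, 79.2% for the third and 77.1% for the fourth, settling at 77.8%. The figure of 78% is therefore an average.

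**Step 5, guessing the next enrollee without tracking order.** With equal use:
- After an odd-numbered participant, the next person is the pair-mate: 7/9.
- After an even-numbered participant, the next person is in the same block only if the broken code was in the first half of a block of 4, which has probability 2/3 × 1/2 = 1/3. This gives 1/3 × 2/3 + 2/3 × 1/2 = 5/9.
- Average: (7/9 + 5/9)/2 = 2/3 = 66.7%.

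**Step 6, larger blocks.** By Step 2, a block of 6 gives 3/5 and a block of 8 gives 4/7. Blocks of 4, 6 and 8 hold 2, 3 and 4 pairs. With equal use of the sizes:
- 4 and 6: (2 × 2/3 + 3 × 3/5)/5 = 62.7%
- 4, 6 and 8: (2 × 2/3 + 3 × 3/5 + 4 × 4/7)/9 = 60.2%

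**The case against.** The strongest reply is that Section 6.3 only contrasts opening one participant's code with opening the whole list, and does not promise that nothing can be inferred about anyone else. Read strictly, every permuted-block design fails, including the larger blocks in Step 6. This stands in part: no block scheme removes the leak. But the sentence is an assurance about the rest of the study, and under every mix of 2 and 4 it fails for at least one other participant at the site.

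Other points against it carry weight:

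- **Few breaks.** Section 6.3 restricts unblinding to emergencies in which treatment knowledge would dictate the action. Section 6.5.1 knows of no specific rescue medicine for the study drug, and Section 7.2 allows study drug to be stopped without unblinding. Each break informs mainly on one other participant.
- **Limited route to the endpoints.** NAD+ and the platelet component are laboratory values. Relatedness is not part of the safety endpoint definition. The blinded committee re-grades unexpected events; its gap is the expected and COVID-related events. Section 10.1.6 describes its remit more broadly, as all reportable events.
- **Enrolment checks.** The treating clinician's permission is sought, and the screening log records why eligible patients were not enrolled (Section 5.4).
- **Timing.** Section 5.5 gives 100 participants, three sites and about 15 months. With equal sites and even accrual, that is about 456 days/33 = 14 days between enrolments at a site. If an even-numbered participant's code is broken, the earlier pair-mate has usually passed Day 10. With random arrivals and a break uniform over Days 0 to 10, the chance of still being in that window is 1 − (14/10)(1 − e^(−10/14)), about 30%. Events are collected to Day 90 (Section 8.3.4), so the pair-mate is usually still under some assessment, but often outside the primary safety period.
- **Manual of operation.** It may already restrict who learns of a code break. That would not undo printing the block sizes in the protocol.

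A reader might infer that each break reveals another participant's arm with 78% certainty, or that the trial's blind is compromised. The documents support neither. The 78% needs equal use of the sizes and someone tracking order; it is an average for one pair-mate; and it describes a guess, not a disclosure.

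**Conclusion.** The point holds as a minor one. The assurance in Section 6.3 does not fit the randomization in Section 9.4.1: a code break raises the chance of guessing the pair-mate's arm from 50% to between 67% and 100%. That range needs no assumption about the mix, but it does assume that someone at the site knows the sizes and follows the order. The averages of about 78% for the pair-mate, and about 67% for the next enrollee without tracking order, both rest on equal use of the two sizes.

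The trial-level effect cannot be sized, because the number of breaks is not given. It is probably small. What remains exposed is site grading of events outside the blinded committee's review, and the decision to enrol the next patient.

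**What to change.** - **Section 9.4.1:** drop the block of 2 and use randomly varied larger blocks within site, for example 4 and 6, or 4, 6 and 8. Remove the sizes from the protocol supplied to sites, and state that the randomization service and the unblinded statistician hold them.
- **Section 6.3:** replace the assurance with a statement that the result of a code break goes only to those who need it and that block sizes are withheld from sites.

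The cost is a change to the randomization settings and a few sentences of text. The worst-case difference in arm counts within a site rises from 2 to 3 (largest block 6) or 4 (largest block 8). The efficiency loss from a difference d at a site of N is (d/N)². With equal sites, N is about 100/3 = 33:

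- d = 2: (2/33)² = 0.4%
- d = 3: (3/33)² = 0.8%
- d = 4: (4/33)² = 1.5%

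Against the stated power above 99.9% for NAD+ (Section 9.2), this is negligible.
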